#### 6.5.1.3 *Pre-Treatment AEs*

Pre-treatment AEs will be summarized by SOC and PT for enrolled subjects (overall, not by treatment group) and the following endpoints:

- AEs by severity (total, mild, moderate, severe, moderate or severe, not reported)
- SAEs.

Pre-treatment AEs will be summarized by SOC and PT for treated subjects by treatment group and overall and the following endpoints:

- AEs by severity
- SAEs.

Pre-rimegepant AEs will be summarized for DB or OL rimegepant treated subjects analogously.

#### 6.5.1.4 *On-Treatment AEs*

##### **DBT Phase**

On-DBT AEs will be summarized by SOC and PT for treated subjects by treatment group for the following endpoints:

- AEs by severity
  - TEAEs by severity
  - TEAEs occurring with  $\geq 2\%$  frequency on rimegepant and greater than placebo after rounding. Percentages will be displayed rounded to integers, and AEs will be displayed in alphabetical order by SOC and PT.
  - AEs related to study drug by severity
  - AEs related to study drug occurring with  $\geq 2\%$  frequency in any treatment group
  - SAEs
  - AEs leading to study drug discontinuation
  - Hepatic-related AEs
  - Hepatic-related AEs leading to study drug discontinuation
  - Additional AEs of special interest: potential drug abuse, CV, and suicidality. Potential drug abuse AEs will be displayed in alphabetical order by severity and PT without SOC
  - Exposure-adjusted multiple occurrences of unique AEs (see Section 7.6.1)
  - Exposure-adjusted multiple occurrences of unique SAEs (see Section 7.6.1)
-

- Exposure-adjusted multiple occurrences of unique SAEs related to study drug (see Section 7.6.1)
- Exposure-adjusted multiple occurrences of unique non-SAEs occurring with  $\geq 5\%$  frequency in any treatment group (see Section 7.6.1).

AEs by severity will also be summarized analogously by subgroup level and overall for all safety subgroups of interest described in Section 6.1.3.2 for each treatment group.

### **DB or OL Rimegepant Phase**

On-DB or OL rimegepant AEs will be summarized by SOC and PT for DB or OL rimegepant treated subjects by treatment group and overall for the same endpoints described above for the DBT phase. Data cuts (e.g.,  $\geq 2\%$ ) will be applied to overall, not each treatment group. Exposure-adjusted multiple occurrences of unique AEs will be presented only by overall.

In addition, on-DB or OL rimegepant AEs will be tabulated by SOC and PT for DB or OL rimegepant treated subjects by subgroup level and overall for all safety subgroups of interest described in Section 6.1.3.3 for the following endpoints:

- AEs by severity
- AEs occurring with  $\geq 5\%$  frequency by severity. The 5% cut applies only to total severity in overall (not in each subgroup level).
- TEAEs by severity
- TEAEs occurring with  $\geq 2\%$  frequency overall after rounding. Percentages will be displayed rounded to integers, and AEs will be displayed in alphabetical order by SOC and PT.
- AEs related to study drug by severity
- SAEs
- AEs leading to study drug discontinuation
- Additional AEs of special interest: hepatic-related AEs; potential drug abuse AEs, cardiovascular AEs, and suicidality AEs. Potential drug abuse AEs will be displayed in alphabetical order by severity and PT without SOC.

### **OLE Phase and On-Treatment Phase (90-Day Safety Update Only)**

On-OL rimegepant AEs will be summarized by SOC and PT for OL rimegepant treated subjects by overall for the following endpoints:

- AEs by severity
- SAEs
- AEs leading to study drug discontinuation.

On-treatment AEs will be summarized analogously for treated subjects.

---

## **OLE Phase**

On-OL rimegepant AEs will be summarized by SOC and PT for OL rimegepant treated subjects by subgroup level and overall for all safety subgroups of interest described in Section 6.1.3.4 for the following endpoints:

- AEs by severity
- AEs occurring with  $\geq 5\%$  frequency by severity. The 5% cut applies only to total severity in overall (not in each subgroup level).
- SAEs
- AEs leading to study drug discontinuation.

On-OL rimegepant AEs will be summarized by SOC and PT for OL rimegepant treated subjects by overall for the following endpoints (see Section 7.6.1):

- Exposure-adjusted multiple occurrences of unique AEs
- Exposure-adjusted multiple occurrences of unique SAEs
- Exposure-adjusted multiple occurrences of unique SAEs related to study drug
- Exposure-adjusted multiple occurrences of unique non-SAEs occurring with  $\geq 5\%$  frequency.

### **6.5.1.5 Follow-up AEs**

Follow-up AEs will be summarized by SOC and PT for follow-up subjects by treatment group and overall for the following endpoints:

- AEs by severity
- SAEs.

### **6.5.1.6 AEs Across All Study Phases Combined**

AEs will be summarized by SOC and PT for treated subjects by treatment group and overall across all safety analysis periods combined for the following endpoints:

- AEs leading to study drug discontinuation
- Hepatic-related AEs leading to study drug discontinuation.

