### 1.2.2 Secondary Objectives

- To compare the efficacy of rimegepant to placebo on the proportion of subjects who have at least a 50% reduction from baseline in the mean number of moderate or severe migraine days per month in the last 4 weeks of the DBT phase.
  - To compare the efficacy of rimegepant to placebo on the reduction from baseline in the mean number of migraine days per month over the entire course of the double-blind treatment phase.
  - To compare the frequency of use of rescue medications between rimegepant and placebo in the last 4 weeks of the DBT phase.
  - To compare the efficacy of rimegepant to placebo on the reduction from baseline in the mean number of migraine days per month in the first 4 weeks of the DBT phase.
  - To evaluate the safety and tolerability of rimegepant.
  - To evaluate the frequency of alanine aminotransferase (ALT) or aspartate aminotransferase (AST) > 3x upper limit of normal (ULN) with concurrent elevations in total bilirubin (TBL) > 2x ULN in subjects treated with rimegepant.
  - To evaluate the frequency of hepatic-related adverse events (AEs) and hepatic-related treatment discontinuations in subjects treated with rimegepant.
-

- To compare the change from baseline in the Migraine-Specific Quality-of-Life Questionnaire (MSQoL) v2.1 restrictive role function domain score at Week 12 of the DBT phase between rimegepant and placebo.
- To compare the change from baseline in the Migraine Disability Assessment (MIDAS) total score at Week 12 of the DBT phase between rimegepant and placebo.

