## 6 STATISTICAL METHODS

### 6.1 General Methods

Refer to the BHV3000 Core SAP for descriptive statistics, counting rules, rounding rules, dictionaries for coding AEs, medical history, and non-study medications, handling duplicate subjects, and examples of complete dates.

Tables will present results by treatment group (i.e., rimegepant and placebo) and overall with the following exceptions:

- Results for enrolled subjects will be presented only by overall without treatment group.
- Exposure, efficacy, and safety results for the DBT phase will be presented only by treatment group without overall.
- Results for follow-up subjects will be presented by 6 groups: rimegepant, placebo, placebo to open-label rimegepant, placebo no open-label rimegepant, double-blind or open-label rimegepant, and overall. “Placebo to open-label rimegepant” denotes as-treated placebo subjects who received open-label rimegepant, and “placebo no open-label

rimegepant” denotes as-treated placebo subjects who never received open-label rimegepant; note that these 2 groups add to the “placebo” group. Also note that the “rimegepant” and “placebo to open-label rimegepant” groups add to the “double-blind or open-label rimegepant” group.

The population samples of treated subjects, OL rimegepant treated subjects, DB or OL rimegepant treated subjects, interim subjects, and follow-up subjects will be assessed by as-treated treatment group, i.e., by the treatment actually received, unless specified otherwise. Otherwise, all other population samples will be assessed by as-randomized treatment group.

All listings except administrative listings will identify subjects who are impacted by COVID-19 (see Section 9.1.2).

Select listings of measurements over time will display COVID-19 visit impact code for visits that are impacted by COVID-19 (see Section 9.1.5.2).

All statistical analyses will be performed using SAS statistical software (Version 9.4 or higher).

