## 6.5 Safety

Safety analyses will be tabulated by as-treated treatment group and overall, unless specified otherwise. Results for treated subjects on DBT will be tabulated by as-treated treatment group without overall treatment group.

Safety outcome measures will include deaths, AEs, laboratory tests, vital signs, physical measurements, electrocardiograms (ECGs), and S-STs.

Safety analysis periods are pre-treatment, pre-rimegepant treatment, on-DBT, on-OL rimegepant, on-treatment (on-DBT and on-OL rimegepant combined), on-rimegepant (DB or OL), post-DBT pre-OL rimegepant, and follow-up (see Section 7.4).

- For the blinded interim analysis in the 90-Day Safety Update, safety analysis periods of primary interest will be on-DBT, on-OL rimegepant, on-treatment, and follow-up.
- For unblinded analyses in CSRs, safety analysis periods of primary interest will be on-DBT, on-rimegepant, and follow-up.

Measurements will be slotted into analysis periods based on “measurement date”, which is (1) imputed start date for AEs, (2) death date for deaths (see Section 7.3), and (3) collection or assessment date for all other safety parameters.

Select safety parameters will be summarized as continuous parameters at baseline and each scheduled visit over time in the various safety analysis periods. Measurements will be slotted into safety analysis periods and analysis windows as follows:

- For treated subjects, measurements will be first slotted into the on-DBT, on-OL rimegepant, and follow-up safety analysis periods. Next, measurements will be slotted into analysis visit windows in these analysis periods.
- For rimegepant treated subjects, measurements will be first slotted into the on-rimegepant and follow-up safety analysis periods (see Section 7.4). Next, measurements will be slotted into analysis visit windows in these analysis periods.

If a subject has multiple values in an analysis visit window in a safety analysis period, then the non-missing value in the analysis period closest to the target date for the visit will be used; in the case of a tie, the latest value collected (from the central laboratory, if applicable) will be used. Results will also be shown at EOT for each phase, i.e., last non-missing measurement in the on-DBT, on-OL rimegepant, and on-DB or OL rimegepant safety analysis periods. Results will also be shown at end of follow-up (EOFU), i.e., last non-missing measurement in the follow-up safety analysis period.

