    - Study drug end date/time: Latest study drug date/time.
    - Study drug last date/time:
      - Interim database lock: Study drug end date/time date derived only for subjects who have either (1) non-missing DB completion status on the DB Subject Status CRF, not continuing to OL on the DB Subject Status CRF, and missing OL rimegepant start date/time, or (2) non-missing OL completion status on the OL Subject Status CRF.
      - Final database lock: Study drug end date/time.
-

- DBT start date/time: Earliest DBT study drug date/time. This should be equal to study drug start date/time.
  - DBT end date/time: Latest DBT study drug date/time.
  - DBT last date/time:
    - Interim database lock or snapshot prior to Week 12 Interim Analysis database lock: DBT end date/time date derived only for subjects with non-missing DB study completion status on DB Subject Status CRF.
    - Database locks at or after Week 12 Interim Analysis database lock: DBT end date/time.
  - OL rimegepant start date/time: Earliest OL rimegepant study drug date/time.
  - OL rimegepant end date/time: Latest OL rimegepant study drug date/time.
  - OL rimegepant last date/time:
    - Database lock or snapshot prior to final database lock: OL rimegepant end date/time date derived only for subjects with non-missing OL study completion status on OL Subject Status CRF or non-missing follow-up study completion status on the Follow-up Subject Status CRF.
    - Final database lock: OL rimegepant end date/time.
  - DB or OL rimegepant start date/time: Study drug start date/time for subjects whose as-treated treatment group is rimegepant; OL rimegepant start date/time for subjects whose as-treated treatment group is placebo.
  - DB or OL rimegepant end date/time: Study drug end date/time for subjects whose as-treated treatment group is rimegepant; OL rimegepant end date/time for subjects whose as-treated treatment group is placebo.
  - DB or OL rimegepant last dose date/time: Study drug last date/time for subjects whose as-treated treatment group is rimegepant; OL rimegepant last date/time for subjects whose as-treated treatment group is placebo.
  - Other eDiary dates:
    - Headache start date/time: Complete reference time point date/time from the headache start question from the evening report headache log.
    - Headache end date/time: Complete reference time point date/time from the headache end question from the evening report headache log or follow-up headache log.

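### The placebo column of the all-phases discontinuation tables includes events on open-label rimegepant and cannot be read as a control

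*SAP*

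**What the plan says.** SAP 6.5.1.6 pools every safety analysis period and reports two endpoints, AEs leading to study drug discontinuation and hepatic-related AEs leading to study drug discontinuation, for "treated subjects by treatment group and overall across all safety analysis periods combined". It gives no further rule for the columns, so the general rules apply.

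- SAP 6.1 sets the default: "Tables will present results by treatment group (i.e., rimegepant and placebo) and overall with the following exceptions".
- SAP 6.5 sets the basis: "Safety analyses will be tabulated by as-treated treatment group and overall, unless specified otherwise".
- The arm label does not change when open-label drug starts. One of the groups in SAP 6.1 "denotes as-treated placebo subjects who received open-label rimegepant". SAP 7.3 likewise takes the start of rimegepant to be the "OL rimegepant start date/time for subjects whose as-treated treatment group is placebo". A subject can therefore be as-treated placebo and also have an open-label start date.
- SAP 6.1 separates these subjects in one place only: "Results for follow-up subjects will be presented by 6 groups: rimegepant, placebo, placebo to open-label rimegepant, placebo no open-label rimegepant". A combined double-blind or open-label rimegepant group and an overall group complete the six. The rule is written for follow-up subjects, whereas 6.5.1.6 uses treated subjects.

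**The concern.** A table with columns headed rimegepant and placebo invites a comparison of drug with control. Here the placebo column holds up to 12 weeks on placebo and then, for those who continue, up to 52 weeks on rimegepant. Events that began on rimegepant are counted under placebo. The absolute figure in that column is not a placebo rate, and the contrast between the columns is pulled towards 1 whatever the drug does.

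The rimegepant column is also incomplete as a count of events on drug, because it leaves out the open-label events of former placebo subjects. The overall column includes time on placebo only. So no column shows events on rimegepant alone and complete.

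The subject makes a misreading costly. Protocol 1.3.1 names change in liver function tests as the main AE of interest, and one of the two tables is about hepatic discontinuations.

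**Working it through.** The documents give no figure for the make-up of this column, so there is none to reproduce. The check takes planned exposure and asks what the column would contain.

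**Inputs from the plan**
- 400 subjects per arm (SAP 5).
- About 675 entering the extension (SAP 2.2).
- 12 weeks double-blind and 52 weeks open-label (SAP 2.1).

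**Assumptions, not in the documents**
- Equal entry by arm: 675 / 2 = 337.5.
- All 400 placebo subjects complete 12 weeks.
- Event rates are constant over time.
- Mean open-label exposure is varied from 13 to 52 weeks.

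**Formulas for the placebo column**
- Placebo time: DB = 400 × 12 = 4,800 person-weeks.
- Open-label rimegepant time: OL = 337.5 × mean open-label weeks.
- Share of on-drug time on rimegepant = OL / (DB + OL).
- With a true rate ratio R (rimegepant to placebo), the rimegepant column has rate R and the placebo column has rate (DB + R × OL) / (DB + OL), in units of the placebo rate. The apparent ratio is R × (DB + OL) / (DB + R × OL).

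| Mean open-label weeks | OL person-weeks | Share on rimegepant | Apparent ratio when R = 2 |
|---|---|---|---|
| 52 | 17,550 | 17,550 / 22,350 = 78.5% | 44,700 / 39,900 = 1.12 |
| 39 | 13,162.5 | 13,162.5 / 17,962.5 = 73.3% | 35,925 / 31,125 = 1.15 |
| 26 | 8,775 | 8,775 / 13,575 = 64.6% | 27,150 / 22,350 = 1.21 |
| 13 | 4,387.5 | 4,387.5 / 9,187.5 = 47.8% | 18,375 / 13,575 = 1.35 |

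At full exposure the apparent ratio has a ceiling of 22,350 / 17,550 = 1.27, however large R becomes.

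**Whether most events in the column arise on rimegepant.** They do if the open-label rate exceeds DB / OL times the placebo rate. That threshold is 4,800 / 17,550 = 0.27 at 52 weeks and 4,800 / 4,387.5 = 1.09 at 13 weeks. If the rate on rimegepant is twice that on placebo, the share of events is 35,100 / 39,900 = 88% at 52 weeks and 8,775 / 13,575 = 65% at 13 weeks.

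**Cross-check with percentages of subjects.** Assume, for illustration only, a risk per 12 weeks of 1% on placebo and 2% on rimegepant. The 52-week risk on rimegepant is 1 − 0.98^(52/12) = 8.38%. The fraction entering the extension is 337.5 / 400 = 0.84375, so the open-label part adds 0.84375 × 8.38% = 7.07 points to each column. The columns read 1% + 7.07% = 8.07% and 2% + 7.07% = 9.07%, a ratio of 1.12 against a true 2.

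**The case against.** The strongest reply is that no conclusion of the plan depends on these tables.

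- SAP 6.5.1.4 tabulates both endpoints for the double-blind period by arm, with no open-label events. It repeats them for the double-blind or open-label rimegepant period, where a placebo-arm subject contributes only from the start of open-label drug.
- SAP 6.5 names the double-blind, on-rimegepant and follow-up periods as those of primary interest in the unblinded reports. The pooled view is not among them, and no test or ratio is attached to it.
- The related secondary objective is "To evaluate the frequency of hepatic-related adverse events (AEs) and hepatic-related treatment discontinuations in subjects treated with rimegepant". It asks for no placebo contrast, and SAP Table 2 defines the endpoint on treatment.
- Listings show the analysis period and the rimegepant study day.
- A pooled table has a fair use as a complete count of discontinuation AEs, and its overall column gives that count.

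All of this stands. It rules out the stronger inference a reader might draw, that the plan hides a drug effect on discontinuation. A second inference, that the placebo column will consist mostly of events on rimegepant, is also not established. It depends on extension exposure, and at an assumed mean of 13 weeks with equal rates the share is below half. The Week 12 analysis for the CSR takes place when the last subject finishes double-blind treatment (SAP 4), so open-label exposure may still be short then.

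Table layout is deferred to the Core SAP and mock table documents, which are not available here, so a clarifying footnote may exist. None of these points makes the placebo column a placebo rate. The phase-specific tables also do not replace the pooled one entirely: the follow-up tables (6.5.1.5) do not report discontinuation AEs, and the gap-period tables (6.5.1.7) do not report hepatic ones separately. Readers who want the full count will therefore come to 6.5.1.6.

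**Conclusion.** The point holds as a misattribution in two supplementary descriptive tables. As specified, the placebo column of SAP 6.5.1.6 mixes two treatments and cannot be read as a control. At planned exposure 78.5% of its on-drug time is on rimegepant, with 47.8% as the low end of the range examined. A true rate ratio of 2 would appear as 1.12 to 1.35 over that range. The mixing follows from the SAP's own column rules. The sizes rest on equal extension entry by arm, constant rates and the assumed open-label exposure, since the documents give no event rates. The randomised comparison for both endpoints is intact in SAP 6.5.1.4, so the documents do not support a claim that safety findings are concealed.

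**What to change.** In SAP 6.5.1.6, present both endpoints in the six groups that SAP 6.1 already defines for follow-up subjects. For placebo subjects who went on to open-label rimegepant, also split the events by treatment at AE onset: before, or on or after, the open-label rimegepant start date. The six groups alone are not enough, because that group still pools its own placebo and rimegepant time, and the combined rimegepant group inherits the mixture. Add a footnote that the undivided placebo column includes events on open-label rimegepant and that any comparison of drug with placebo should be taken from the double-blind tables in 6.5.1.4.

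The cost is a sentence or two in the SAP, a few extra columns in two tables and a footnote. The open-label start date is already derived in SAP 7.3, so no new data are needed.

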### **6.5.1.7 Post-DBT Pre-OL Rimegepant AEs**

Post-DBT pre-OL rimegepant AEs will be summarized by SOC and PT for interim subjects by treatment group and overall for the following endpoints:

- AEs by severity
  - SAEs
-

- AEs leading to study drug discontinuation.

### **6.5.2 Laboratory Tests**

Clinical safety laboratory testing will be performed at early termination and the following visits: screening; baseline; Weeks 4, 8, and 12 of the DBT phase; and Weeks 16, 24, 48 and 64 of the OLE phase. Urinalysis will be collected at early termination and the following visits: baseline; and Weeks 24 and 64 of the OLE phase. Lipids (i.e., cholesterol, high-density lipoprotein (HDL) cholesterol, low-density lipoprotein (LDL) cholesterol, and triglycerides) will be collected at early termination and the following visits: baseline; and Weeks 24 and 64 of the OLE phase. LFTs (ALT, AST, alkaline phosphatase [ALP], TBL, and direct bilirubin) will be collected routinely at early termination and the following visits: screening; pre-randomization lab visit; baseline; Weeks 2, 4, 8, and 12 of the DBT phase; Weeks 14, 16, and every 4 weeks through Week 64 of the OLE phase; and follow-up Weeks 2 and 8.

Clinically significant laboratory abnormalities will be identified as grade 3 to 4 laboratory test results. Refer to the BHV3000 Core SAP for laboratory tests of clinical interest and toxicity grading. Laboratory test groups of clinical interest will include hematology, serum chemistry, and urinalysis.

LDL cholesterol and triglycerides will be analyzed as separate laboratory test parameters according to fasting status: fasting (i.e., fasting status of yes), not fasting (i.e., fasting status not equal to yes, including no, unknown, not reported, missing, etc.), and overall.

Estimated glomerular filtration rate (eGFR) will be derived using the modification of diet in renal disease (MDRD) formula; refer to the BHV3000 Core SAP for additional details.

Tables, listings, and figures (TLFs) will be provided to show data in both Systeme Internationale (SI) and United States (US) unit systems, if applicable.

Tables will present results by treatment group (and overall if applicable), and laboratory tests alphabetically within laboratory test group, as applicable.

By-subject listings of the following select laboratory test will be provided for enrolled subjects: hematology; serum chemistry (including eGFR derived using MDRD); urinalysis (US units only); pregnancy (US units only); endocrinology, serology, drug screen, and miscellaneous laboratory tests (US units only); and local laboratory CK fractionation. In addition, a by-subject listing of LFT values and ratios to ULN (i.e., ALT, AST, TBL and ALP) will also be provided for enrolled subjects, which will include all results over time for those with select elevations (ALT or AST > 3 x ULN; ALP or TBL > 2 x ULN) at any time point. COVID-19 visit impact code for visits impacted by COVID-19 will be displayed for each laboratory test of clinical interest in the following listings: hematology; serum chemistry; urinalysis; pregnancy (urine tests only); and LFT values and ratios to ULN. Refer to the BHV3000 Core SAP for listing content.

